6.4.3.1 Adverse Events Based on Signs and Symptoms

All AEs spontaneously reported by the subject or reported in response to the open question from the study personnel or revealed by observation will be collected and recorded in the eCRF. When collecting AEs, the recording of a diagnosis is preferred (when possible) to the recording of a list of signs and symptoms. However, if a diagnosis is known and there are other signs or symptoms that are not generally part of the diagnosis, the diagnosis and each sign or symptom will be recorded separately.

6.4.3.2 Adverse Events Based on Examinations and Tests

If an abnormal laboratory value/vital sign is associated with clinical signs and symptoms, the sign or symptom will be reported as an AE and the associated laboratory result/vital sign will be considered as additional information. Wherever possible the reporting investigator uses the clinical rather than the laboratory term (e.g., anemia vs low hemoglobin value). In the absence of clinical signs or symptoms, clinically significant findings on examinations and tests should be reported as AEs.

Any new or aggravated clinically significant abnormal medical finding at a physical examination as compared with the baseline assessment will be reported as an AE.

6.4.3.3 Pericarditis Disease Related Events

Signs, symptoms, and abnormal findings associated with pericarditis are to be captured as a pericarditis recurrence event rather than as an AE unless the event is more severe than expected for the subject. In any case, pericarditis recurrence is required to be captured in the eCRF (see [Section 6.2.3](#)) within 24 hours of learning of the event.

6.4.4 Time Period for Collection of Adverse Events

Adverse events will be assessed from the time the subjects signs the ICF and through the duration of the study, or at least through the SFU period (6 weeks after the last dose of study drug).

6.4.5 Follow-Up of Unresolved Adverse Events

Every reasonable effort will be made to follow subjects who have AEs.

Any AEs that are unresolved at the subject's SFU visit are to be followed up by the investigator until resolution or for as long as medically indicated. Additional information for any subject with an ongoing AE at the end of the SFU period may be requested by the [REDACTED] PHV, as needed.

6.4.6 Reporting Serious Adverse Events

Any AE that meets SAE criteria ([Section 6.4.1.3](#)) must be reported to the [REDACTED] PHV using the EDC system, immediately (i.e., within 24 hours) after the time site personnel first learn about the event.

In the event the EDC entry is not possible (e.g., system failure or access problems), the study site should complete the paper SAE report form and fax the form to the [REDACTED] PHV within 24 hours of awareness. The EDC system should be updated as soon as it is available.

A full description of every SAE will need to be provided to the [REDACTED] PHV (this may be supported by source documentation such as discharge summary or laboratory report should these documents be requested by the [REDACTED] PHV). Additional follow-up information, if required or available, should be sent to the [REDACTED] PHV as soon as possible and placed with the original SAE information.

Any SAE occurring in association with a pregnancy, brought to the investigator's attention after the subject has completed the study, and considered by the investigator as possibly related to the study drug, must be promptly reported to the [REDACTED] PHV.

In the event that a subject is found to be pregnant after having received at least 1 study drug dose, the study drug must be discontinued, and the pregnancy will be followed to term and the status of mother and child will be reported to the [REDACTED] PHV after delivery. Instances of perinatal death or congenital abnormality, if brought to the attention of the investigator at any time after cessation of study drug, will be reported to the [REDACTED] PHV within 24 hours.

6.4.8 Evaluating and Reporting SUSARs

[REDACTED] Pharmacovigilance will promptly evaluate all SUSARs and nonserious AEs of special interest against cumulative product experience to identify and expeditiously communicate possible new safety findings to investigators, IRBs/IECs, and applicable health authorities based on applicable legislation.

To determine reporting requirements for single AE cases, [REDACTED] PHV staff in collaboration with Kiniksa Pharmaceuticals will assess the expectedness of these events using the Reference Safety Information (Section 6.2) of the rilonacept Investigator's Brochure.

[REDACTED] PHV will compare the severity of each SUSAR and the cumulative event frequency reported for the study with the severity and frequency reported in the applicable reference document.

Reporting requirements will also be based on the investigator's assessment of causality and seriousness, with allowance for upgrading by [REDACTED] PHV and Kiniksa Pharmaceuticals as needed.

All relevant information about suspected SUSARs that are fatal or life-threatening will be recorded and reported to the competent authorities in all the applicable countries, and IRBs/IECs in conjunction with Directive 2001/20/EC.

6.5 Other Assessments

6.5.1 Pharmacokinetic Sample

All subjects will have PK samples obtained according to the [Study Schedule of Activities](#). For PK analyses, it is important that the exact time of the SC injection is recorded for each subject. When PK samples are to be collected on dosing days, serum will be collected pre-dose to measure rilonacept concentrations. Specific procedures for sample collection, processing, storage, and shipment can be found in a separate Laboratory Manual provided to sites.

A PK substudy will be conducted in a subset of subjects agreeing to provide a PK sample 24 hours after the first dose of study drug in the RI period. Specific procedures for sample collection, processing, storage, and shipment can be found in a separate Laboratory Manual provided to sites.

6.5.2 Anti-Drug Antibodies (ADAs) against Rilonacept (KPL-914)

Serum samples to measure the presence of ADAs against rilonacept will be collected according to the [Study Schedule of Activities](#). Instructions for sample collection, processing, storage, and shipment can be found in a separate Laboratory Manual provided to the site.

6.5.3 Biomarkers

Serum and plasma will be collected according to the Study Schedule of Activities for biomarker analysis.

6.5.4 Pharmacogenomics

Whole blood will be collected for pharmacogenomics assessments after signing the separate Pharmacogenomics ICF.

6.6 Laboratory Analyses

Any abnormal laboratory test results (hematology, chemistry, or urinalysis) or other safety assessments (e.g., physical examination, vital signs measurements), including those that worsen from baseline, felt to be clinically significant in the medical and scientific judgement of the investigator are to be recorded as AEs or SAEs.

Laboratory assessments will be performed at study visits as summarized in Study Schedule of Activities. Unscheduled laboratory assessments for safety issues are permitted as deemed necessary by the investigator.

Whenever possible in pediatric subjects, local laboratory tests should be drawn using pediatric tubes.

6.6.1 Serology

Samples for local laboratory assessment of hepatitis B surface antigen, hepatitis B core antibody, hepatitis C virus antibody, and HIV levels will be collected at screening. If clinically indicated, those tests may be also collected during the study.

6.6.2 Hematology

Hematology tests performed at central study laboratory include WBC count with differential, platelet count, red blood cell count, mean corpuscular volume, hemoglobin, mean corpuscular hemoglobin concentration.

6.6.3 Chemistry

Blood chemistry tests performed in the central study laboratory include albumin, total protein, alkaline phosphatase, ALT/SGPT, AST/SGOT, direct bilirubin, total bilirubin, bicarbonate, chloride, potassium, sodium, creatinine, glucose.

In addition, the following chemistry tests may be performed together with local CRP measurement when using POC device: chloride, creatine kinase, creatinine, glucose, potassium, sodium, total carbon dioxide, blood urea nitrogen.

6.6.4 Non-fasting Lipid Panel

Subjects treated with rilonacept may experience increases in their lipids, including total cholesterol, LDL, HDL, and triglycerides.

Non fasting measurements of total cholesterol, triglycerides, HDL, and direct LDL will be performed by central study laboratory as described in the [Study Schedule of Activities](#).

Investigators should monitor the lipid profiles in study subjects and consider ordering fasting lipid panel and/or lipid lowering therapies as needed based on cardiovascular risk factors and current guidelines.

6.6.5 Urinalysis

Urinalysis performed by the central study laboratory includes specific gravity, pH, protein, urobilinogen, ketones, glucose, blood, bilirubin, nitrites, leukocyte esterase. It will be performed as described in the [Study Schedule of Activities](#).

6.6.6 Pregnancy Test

For women of child-bearing potential, a urine pregnancy test using a licensed test (dipstick) should be performed prior to receiving the first administration of study drug, and as needed during the study, and also at the SFU visit. When needed, serum pregnancy test should be performed. The purpose of pregnancy test is to prevent embryo/fetal exposure to study drug. Subjects with positive or indeterminate pregnancy test during the screening are not eligible for the study.

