^h Lipid panels are non-fasting and are to be drawn at a minimum of every 6months during the randomization withdrawal and LTE periods, or more frequently as needed, with mandated evaluations as detailed in the schedule of events.

^j For women of child bearing potential - urine pregnancy testing can be repeated as needed throughout the course of the study and serum pregnancy can be drawn as needed; urine pregnancy is required to be performed at enrollment and 6 weeks after the last dose of study drug.

^l Adverse event reporting begins following the subject providing informed consent.

^m All procedures are to be completed prior to study drug administration.

^o Study drug administration is once weekly with a minimum of 5 days required between doses.

^t The EORW visit serves as both the last visit of the RW period and the baseline visit of the LTE period.

^u For all subjects, the final clinic visit of the end of RW period is to be scheduled once the End of the Randomization Withdrawal end date is announced by Sponsor. This includes subjects that are taking blinded study drug, open-label rilonacept, or who have prematurely discontinued study drug.

^v Study drug administration to occur only after subject provides informed consent for the open-label extension period.

Table 1–3 Study Schedule of Activities – Long Term Extension (Part 1 of 2)

Trial Period	LONG TERM EXTENSION (48 WEEKS)				
	Long Term Extension Treatment (24 Weeks) ^m			Long Term Extension Follow Up (24 Weeks)	
Visit Name	LTE Week 8	LTE Week 16	LTE Week 24	LTE Week 30	EOS/ LTE Week 48
Visit Window ^b (days)	+/- 2	+/- 2	+/- 2	+/- 2	+/- 2
Visit Type	Clinic	Clinic	Clinic	Clinic	TC
Concomitant medications	X	X	X	X	X
Pericarditis Concomitant medications	X	X	X	X	X
Full Physical Examination ^c			X		
12-Lead ECG			X		
Echo ^e			X		
MRI (substudy only)			X		
Pericardial pain (11-point NRS)	DAILY				
EQ-5D			X		
SF-36			X		
ISI			X		
PGIPS	X	X	X		
PGA-PA	X	X	X		

^b Scheduling of visits within visit windows requires cautious planning to ensure there is no interruption to subject evaluation and study drug treatment.

^c Full physical examination includes at minimum evaluation of vital signs, head, eye, ear, nose, and throat as well as cardiovascular, dermatological, musculoskeletal, respiratory, GI, genitourinary, and neurological systems

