The impact of treatment with rilonacept on the development of malignancies is not known. However, treatment with immunosuppressants, including rilonacept, may result in an increase in the risk for malignancies.

Fetal Defects

There are no adequate and well-controlled studies of rilonacept in pregnant women. Based on animal data, rilonacept may cause fetal harm. An embryo-fetal developmental toxicity study was performed in cynomolgus monkeys treated with 0, 5, 15, or 30 mg/kg given twice a week (highest dose is approximately 3.7-fold higher than the human dose of 160 mg based on body surface area). The fetus of the only monkey with exposure to rilonacept during the later period of gestation showed multiple fusion and absence of the ribs and thoracic vertebral bodies and arches. Exposure to rilonacept during this time period was below that expected clinically. Likewise, in the cynomolgus monkey, all doses of rilonacept reduced serum levels of estradiol up to 64% compared to controls and increased the incidence of lumbar ribs compared to both control animals and historical control incidences. In perinatal and postnatal developmental toxicology studies in the mouse model using a murine analog of rilonacept (0, 20, 100, or 200 mg/kg), there was a 3-fold increase in the number of stillbirths in dams treated with 200 mg/kg 3 times per week (the highest dose is approximately 6-fold higher than the 160 mg maintenance dose based on body surface area).

Nonteratogenic effects: A peri- and postnatal reproductive toxicology study was performed in which mice were administered a murine analog of rilonacept at doses of 20, 100, and 200 mg/kg SC 3 times per week (the highest dose is approximately 6-fold higher than the 160 mg maintenance dose based on body surface area). Results indicated an increased incidence in unscheduled deaths of the F1 offspring during maturation at all doses tested.

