4.2 Subject Completion, Withdrawal from Study, and Study Drug Discontinuation

4.2.1 Completion

A subject will be considered to have completed the study if she/he has completed the RW period and has completed assessments at the EORW visit. At the EORW visit, subjects who were randomly assigned to rilonacept or subjects who transitioned to open-label rilonacept upon protocol-defined pericarditis recurrence (Section 6.2.3) in the RW period will be offered an opportunity to receive an additional 24 weeks of open-label rilonacept treatment based on their clinical status and at the discretion of the investigator, and after signing the LTE informed consent.

At the EORW visit, subjects who were randomly assigned to placebo and did not transition to bailout rilonacept will be offered an opportunity to receive an additional 24 weeks of open-label rilonacept treatment based on their clinical status and at the discretion of the investigator, after signing the LTE informed consent.

Any subject who in the opinion of investigator should not continue open-label rilonacept in LTE will be offered the opportunity to continue follow-up off study drug treatment in LTE, after signing the LTE informed consent.

Subjects who elect not to enter LTE will be followed for 6 weeks after receiving the last study drug administration.

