5.2 Treatments Administered

Throughout this protocol, “study drug” refers to the investigational medicinal products: rilonacept and matching placebo. Both will be administered as applicable by SC injection.

Study drug administration will be performed once a week (every 7 ± 2 days). The interval between study drug administrations must be at least 5 days.

Study drug will be dosed as follows:

Adult Subjects (≥ 18 years old):

Rilonacept: Loading dose 320 mg administered as 2 SC injections, 160 mg each (2 ml) at RI baseline, followed by once-weekly SC injections of 160 mg (2ml).

Placebo: administered as once-weekly SC injections of 2 ml each in the RW period

Upon meeting protocol criteria for bailout rilonacept ([Sections 3.1](#) and [6.2.3](#)) in the RW period, subjects will be transitioned to open-label rilonacept 320 mg administered as 2 SC injections, 160 mg each (2 ml) at the next scheduled study drug administration date, followed by once-weekly SC injections of 160 mg (2ml).

Pediatric Subjects (≥ 12 and < 18 years old):

Rilonacept: Loading dose 4.4 mg/kg administered as 2 SC injections, 2.2 mg/kg each (maximum 160 mg each) at RI baseline, followed by once-weekly SC injections of 2.2 mg/kg (maximum 160 mg). The volume of injections will be based on the subject’s weight ([Table 5–1](#)).

Placebo (in RW): once-weekly SC injections with volume based on the subject’s weight ([Table 5–1](#), maximum 2 ml).

Upon meeting protocol criteria for bailout rilonacept ([Sections 3.1](#) and [6.2.3](#)) in the RW period, subjects will be transitioned to open-label rilonacept 4.4 mg/kg administered as 1 (maximum 2 ml) or 2 SC injections at the next scheduled study drug administration date, followed by once-weekly SC injections of 2.2 mg/kg (maximum 2 ml). The volume of injections will be based on the subject’s weight ([Table 5–1](#)).

Study drug dose/volume will be calculated by the investigator or pharmacist during site clinic visits based on body weight (as specified in the [Study Schedule of Activities](#)) using a weight-based dosing chart in **kilograms** ([Table 5–1](#)).

Table 5–1: Study Drug Dose Volume (After Reconstitution) by Body Weight in Kilograms for Pediatric Subjects Aged ≥ 12 and < 18 Years

Weight Range (kg)	Loading Dose Volume (ml)	Weekly Dose Volume (ml)
23.6 to 27.2	2 x 0.7	0.7
27.3 to 30.8	2 x 0.8	0.8
30.9 to 34.4	2 x 0.9	0.9
34.5 to 38.1	2 x 1.0	1.0
38.2 to 41.7	2 x 1.1	1.1
41.8 to 45.4	2 x 1.2	1.2
45.5 to 49.0	2 x 1.3	1.3

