6.1.6 Supplemental Visits

6.1.6.1 Pericarditis Recurrence Assessment: Clinic Visit

If a subject experiences symptoms consistent with pericarditis recurrence, he/she should contact the study investigator immediately for evaluation. It is possible that a subject may have assessments performed remotely, however, assessments are also expected to be performed at the study site as soon as possible. Required assessments include:

- Evaluate pericarditis pain on the 11-point NRS.
- Evaluate concomitant medications as well as pericarditis concomitant medications.
- Obtain laboratory samples for CRP (local and central) (the POC device provided by Kiniksa Pharmaceuticals is the preferred method for local laboratory CRP assessment).
- Acquire a 12 lead ECG.
- Acquire a cardiac ECHO per core laboratory imaging parameters; this ECHO is read locally for the purpose of pericarditis recurrence assessment and is then submitted to the ECHO core laboratory for central review.
- Perform an abbreviated physical examination, height and body weight.
- For subjects >18 years, complete the SF 36, EQ-5D 5L, ISI.
- For all subjects, complete the PGIPS score.
- The investigator is to complete the PGA PA.
- Obtain central laboratory samples for PK, ADAs, and biomarkers.
- Other procedures deemed necessary per the investigator or delegated site personnel.

Upon having completed the evaluation, if the investigator makes a clinical diagnosis that the subject is having a pericarditis recurrence event, he/she should contact the [REDACTED] medical monitor to review and confirm that all assessments have been performed and collected. Upon [REDACTED] medical monitor confirmation of completion of the assessment, the investigator commences as described in [Section 6.2.3](#).

Subjects treated for a pericarditis recurrence event will continue to follow the same visit schedule described for the RW period ([Section 6.1.3](#)).

Source documentation including the assessments and evaluations used to confirm a pericarditis recurrence event, are required to be sent to CEC.

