6.2.3 Management of Suspected Pericarditis Recurrence in the RW Period

Pericarditis Recurrence Definition: Pericarditis recurrence, for the purpose of the protocol, is defined as the recurrence of typical pericarditis pain associated with supportive objective evidence of pericarditis.

At any time point during the RW period, subjects who experience suspected recurrence of their pericarditis will have been instructed to inform their site investigator as soon as possible. Subjects who experience a suspected recurrence of pericarditis symptoms will be requested to report to the study site/clinic for a scheduled or unscheduled visit, during which clinical assessments will be performed to gather all the necessary diagnostic data to confirm or rule out the presence of pericarditis recurrence (Section 6.1.6.1). The investigator will evaluate all assessments performed for a diagnostic workup, whether at the study site or at locations outside.

Upon completion of pericarditis workup, the investigator is required to contact the [REDACTED] medical monitor to confirm that the protocol required diagnostic workup is complete prior to implementing treatment for the event.

Following communication with the [REDACTED] medical monitor, if the event meets the criteria for bailout rilonacept (at least 1 day with pericarditis pain measurement ≥ 4 on the 11-point NRS and one CRP value ≥ 1 mg/dL either on the same day or separated by no more than 7 days), and after the [REDACTED] medical monitor has confirmed with the investigator that the diagnostic workup is complete, the attainment of bailout criteria is confirmed in the IWRS, blinded study drug is discontinued, and open-label rilonacept treatment is dispensed. If needed, sequential ORT is allowed as outlined in Section 5.8.3. The subject will continue to be followed up according to the Study Schedule of Activities for the RW period.

[figure not shown]
Following communication with the [REDACTED] medical monitor, if the event does not meet the protocol criteria for bailout rilonacept but in the judgement of investigator requires treatment, after the [REDACTED] medical monitor has confirmed with the investigator that the diagnostic workup is complete, the investigator is allowed to add sequential ORT to blinded study drug, and as outlined in Section 5.8.3. Blinded study drug treatment will continue until a pericarditis recurrence that meets criteria for bailout rilonacept, or until the end of the RW period.

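### No pregnancy test is required before a placebo subject restarts rilonacept, and criterion 8c counts a partner's vasectomy as the woman's own sterility

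*Protocol*

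**What the plan says.** Section 6.6.6 gives the aim of testing: "The purpose of pregnancy test is to prevent embryo/fetal exposure to study drug". The same section asks for a test before the first dose and at the safety follow-up visit, and otherwise as needed. Footnote j to the schedule tables agrees: "urine pregnancy is required to be performed at enrollment and 6 weeks after the last dose of study drug". Table 1-1 marks the test at screening and RI baseline. In Table 1-2 the pregnancy row is empty in every RW column, including EORW. In Table 1-4 the only mark is under safety follow-up. For subjects in the LTE the test falls at LTE Week 30 (Table 1-3, Section 6.1.5.1).

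The protocol provides two points at which a placebo subject goes back on rilonacept:

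- **Bailout.** Under Section 5.2, adult "subjects will be transitioned to open-label rilonacept 320 mg administered as 2 SC injections", with a weight-based equivalent for adolescents.
- **EORW/LTE baseline.** Under Section 4.2.1, "subjects who were randomly assigned to placebo and did not transition to bailout rilonacept will be offered an opportunity to receive" a further 24 weeks of open-label drug.

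On fetal risk, Section 1.3.1 states: "Based on animal data, rilonacept may cause fetal harm".

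Inclusion criterion 8 gives four alternative ways for a woman to qualify, joined by OR. Item 8c covers permanent sterility after listed surgical procedures, then adds a vasectomised male partner on the subject's word. Item 8d, for women of childbearing potential, is the only one that imposes contraception.

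**The concern.** A test taken 6 weeks after the last dose can reveal an exposure but cannot prevent one. The only required tests that serve the aim in Section 6.6.6 are therefore those before the first run-in dose. For a placebo subject there is a second start of the drug, after a period off it, and no required test stands in front of it. An unrecognised pregnancy at that moment is caught only if someone suspects it.

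Criterion 8c widens the gap. A partner's vasectomy leaves the woman's own fertility unchanged. Because 8a to 8d are alternatives, she qualifies without committing to contraception, and her protection lapses if, for example, her partner changes. Testing is limited to women of childbearing potential, so she can also be read as falling outside it. For male subjects, criterion 9 treats vasectomy as an alternative to birth control and requires it to be documented.

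**Working it through.** The protocol gives no figure for this point, so there is none to reproduce. The check compares the visit lists with the restart points and then adds up the protocol's own period lengths.

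**Is a test required at either restart?**

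- Recurrence visit (Section 6.1.6.1): pain score, medications, local and central CRP, ECG, echocardiogram, abbreviated examination, questionnaires, and "Obtain central laboratory samples for PK, ADAs, and biomarkers". There is no pregnancy test.
- Check before bailout (Section 6.2.3): the investigator contacts the medical monitor to "confirm that the protocol required diagnostic workup is complete prior to implementing treatment for the event". That workup contains no pregnancy test, so the check cannot reveal its absence.
- EORW/LTE baseline (Section 6.1.3.2): the laboratory list includes urinalysis but no pregnancy test.

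The text is the same in both protocol versions in the file (1.0 and 1.1).

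**How old is the last required test?** Inputs: run-in 12 weeks; RW at least 24 weeks; LTE treatment 24 weeks; follow-up test 6 weeks after the last dose; placebo median time to recurrence 8 weeks, exponential (Section 7.4). Weeks are nominal, before visit windows, and counted from the RI baseline test.

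- Placebo restart at EORW: 12 + 24 = 36 weeks at minimum.
- Placebo restart at bailout, at the assumed median: 12 + 8 = 20 weeks.
- Quartiles of an exponential with median 8: 8 × log2(4/3) = 3.3 and 8 × log2(4) = 16, so 12 + 3.3 = 15.3 weeks and 12 + 16 = 28 weeks.

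**How far apart are required tests in general?**

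- Subject completing LTE treatment: 12 + 24 + 24 + 6 = 66 weeks at minimum.
- Subject declining the LTE, with EORW falling at RW Week 24: footnote v to Table 1-2 says "Study drug administration to occur only after subject provides informed consent for the open-label extension period", so her last dose is at about RW Week 23, and 12 + 23 + 6 = 41 weeks.

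These two figures apply to either arm; they describe the testing schedule, not restart.

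**How many placebo subjects could restart?** With 25 placebo subjects, a median of 8 weeks and no dropout:

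- Recurrence by RW Week 24: 1 − 0.5^(24/8) = 0.875, and 25 × 0.875 = 21.9. These subjects reach bailout if they meet the pain and CRP criteria.
- The rest: 25 × 0.125 = 3.1. These can be offered rilonacept at EORW.

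The share who are women of childbearing potential is not given. Assuming 10% to 50%, 25 × 0.10 = 2.5 and 25 × 0.50 = 12.5, or about 3 to 12 women. This counts women who would be tested, not pregnancies.

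**The case against.** The schedule does not contradict itself. Sections 6.3 and 6.6.6, footnote j and the visit lists agree, and repeat tests are allowed at any time. The appended label lists no contraindications, places the drug in Pregnancy Category C and asks for no pregnancy test in its pregnancy section. The protocol goes further: tests at entry, contraception under 8d, exclusion of planned pregnancy, non-leading questions at every visit, and a stopping rule for pregnancy. Starting drug at EORW also needs a new consent and an investigator's decision. Women in the rilonacept arm are dosed through the same weeks with no required test, so a consistent critic would ask for periodic testing. On 8c, a woman who qualifies that way does have a vasectomised partner at entry, remains bound by the exclusion and the stopping rule, and nothing says outright that she skips testing.

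Most of this is accurate, and it keeps the point modest. The 41- and 66-week intervals should not be read as restart figures, and the count of women rests on an assumed share, no dropout and no one declining the LTE. What the objection does not supply is a test before re-dosing. The stopping rule works only once a pregnancy is known, and neither consent nor clinical judgement detects one. The rilonacept arm's lack of mid-study tests is a wider gap, but restart is where a test can still prevent a new exposure. The doubt over how 8c women are classified is itself a reason to correct the wording.

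**Conclusion.** The point holds in both parts. The required schedule leaves the aim of Section 6.6.6 to discretion at the two moments when a placebo subject is re-exposed, with the last required test at least 36 weeks old at EORW and about 20 weeks old at bailout (interquartile range about 15 to 28). The bailout timing rests on the protocol's exponential 8-week median and on restart promptly after recurrence; the EORW figure rests only on period lengths. Criterion 8c misclassifies a fertile woman whatever those assumptions are. No pregnancy probability is estimated and none is needed: the case rests on a stated fetal risk, a stated purpose and the low cost of meeting it. Nothing here touches alpha, power or the primary estimate. It is a cheap improvement that should be made.

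**What to change.** Require a urine dipstick for every woman of childbearing potential at the recurrence assessment, before bailout rilonacept is dispensed, and at EORW/LTE baseline, before the first LTE dose. Add it to Sections 6.1.3.2, 6.1.6.1 and 6.6.6, to the pregnancy rows of Tables 1-2 and 1-4, and to footnote j. Applying it in both arms leaves the blind untouched. A test at RI Week 12 is optional.

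Move the vasectomised-partner wording from 8c to 8d as a contraceptive method, so that these women count as of childbearing potential, carry the contraception commitment and are tested.

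The cost is one dipstick at each of two clinic visits that already take place, plus one wording change. EORW already collects urine; the recurrence visit would need a urine sample. No visits are added, and the burden on the women concerned is minor.
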